10.2.2 Pharmacodynamics/kinetics

Absorption: Following IV administration of fluorouracil, no intact drug is detected in plasma after 3 hours.

Distribution: Fluorouracil is distributed into tumors, intestinal mucosa, bone marrow, liver, and other tissues. Despite its limited lipid solubility, the drug readily crosses the blood-brain barrier and distributes into CSF and brain tissue. Distribution studies in humans and animals have usually shown a higher concentration of the drug or its metabolites in the tumor than in surrounding tissue or in corresponding normal tissue. It has also been shown that there is a longer persistence of fluorouracil in some tumors than in the normal tissues of the host, perhaps due to impaired uracil catabolism. From these data, it has been suggested that the drug may possibly have some specificity against certain tumors in comparison with normal tissues.

Elimination: Following IV administration, the plasma elimination half-life averages about 16 minutes (range: 8-20 minutes) and is dose dependent. A small portion of fluorouracil is anabolized in the tissues to 5-fluoro-2-deoxyuridine and then to 5-fluoro-2-deoxyuridine-5-monophosphate, the active metabolite of the drug. The major portion of the drug is degraded in the liver. The metabolites are excreted as respiratory carbon dioxide and as urea, α -fluoro- β -alanine, α -fluoro- β -guanidopropionic acid, and α -fluoro- β -ureidopropionic acid in urine. Following a single IV dose of fluorouracil, approximately 15% of the dose is excreted in urine as intact drug within 6 hours; over 90% of this is excreted in the first hour.

10.2.3 Availability

Fluorouracil is commercially available as a 50 mg/mL solution for injection in 10 mL, 20 mL, 50 mL and 100 mL vials.

10.2.4 Supplier(s)

5-FU is commercially available and will not be provided by this study.

10.2.5 Solution Preparation

Inspect for precipitate; if found, agitate or gently heat in water bath. Bolus injections are prepared using undiluted drug. Continuous infusions of fluorouracil should be prepared for administration via ambulatory infusion pump according to the individual institution's standards. These solutions may be prepared in D5W or 0.9% NaCl.

10.2.6 Storage and Stability

Intact vials should be stored at room temperature and protected from light. Slight yellow discoloration does not usually indicate decomposition. 5-FU is stable in syringes for up to 72 hours. Stability in ambulatory pumps varies according to the pump, manufacturer of drug, concentration and dilution. Please refer to appropriate reference sources for additional information.

10.2.7 Administration

Fluorouracil will be given as a 400 mg/m² IV bolus injection followed by 2400 mg/m² continuous IV infusion over 46 hours.

10.3 Oxaliplatin

10.3.1 Mechanism of action

Oxaliplatin is a new platinum derivative with an oxalo ligand group. Although the exact mechanism of oxaliplatin's action remains unclear, the cytotoxicity of platinum compounds is thought to result from inhibition of DNA synthesis. Intrastrand platinum DNA adducts, the main cytotoxic lesions, are formed by cross-linking activated platinum species and specific base sequences, notably 2 adjacent guanine residues or 2 adjacent guanine-adenine bases.

10.3.2 Pharmacodynamics/kinetics

Time to peak concentration with a single 2-hour infusion of oxaliplatin 85 milligrams/square meter yielded a peak plasma concentration (C_{max}) of 0.814 micrograms/milliliter. The area under the curve for total plasma platinum was 207-

290 mg/L x hr; ultrafilterable plasma platinum was 11.9-13.6 mg/L x hr. Oxaliplatin has 70 to 95% platinum-protein binding while 37% represents total platinum taken up by red blood cells (addition of oxaliplatin to whole blood). The volume of distribution is 440 liters after a single 2-hour infusion of 85 milligrams/square meter oxaliplatin. Oxaliplatin undergoes rapid and extensive (30%) nonenzymatic biotransformation. In vitro studies indicate no cytochrome P450-mediated metabolism. Oxaliplatin metabolites include approximately 17 different platinum containing derivatives with some being cytotoxic (monochloro DACH platinum, dichloro DACH platinum, and monoquo and diaquo DACH platinum). Breast milk – It is not known whether oxaliplatin is excreted into breast milk. Renal clearance is 9.3-17 liters/hour. Elimination half life: intravenous, total plasma platinum, alpha half-life (0.2-0.43 hours), beta half-life (15-16.8 hours), gamma half-life (252-391 hours). The decline of ultrafilterable platinum levels is triexponential with a relatively short alpha and beta half-life (0.43 hours and 16.8 hours) and a long terminal gamma half-life (391 hours).

10.3.3 Formulation

Molecular formula: $C_8H_{14}N_2O_4Pt$ with the chemical name of cis-[(1R, 2R)-1,2 cyclohexanediamine-N, N'] [oxalato (2-)-o, o'] platinum. Molecular weight is 397.3.

10.3.4 Availability

Oxaliplatin is formulated as a white freeze-dried powder in amber glass vials containing 50 mg and 100 mg of oxaliplatin in lactose monohydrate. Each vial is sealed with a stopper with a crimped aluminum cap. Drug will be ordered from commercial supply.

10.3.5 Supplier(s)

Oxaliplatin is commercially available and will not be provided by this study.

10.3.6 Solution Preparation

The freeze-dried powder is reconstituted by adding 10 to 20 ml (for the 50-mg vial) or 20 to 40 ml (for the 100-mg vials) of sterile water for Injection or 5% dextrose solution and then by diluting in an infusion solution of 250 ml or 500 ml of 5% dextrose solution. Avoid performing these manipulations with aluminum needles. The reconstitution or final dilution must never be performed with a sodium chloride solution.

10.3.7 Storage and Stability

Oxaliplatin freeze-dried powder may be stored at room temperature protected from light. Do not combine with alkaline medications or media, which cause oxaliplatin

to degrade. Do not use needles or intravenous infusion sets containing aluminum items (risk of degradation of oxaliplatin upon contact with aluminum) for the preparation or administration of oxaliplatin. Do not mix oxaliplatin with sodium chloride or other chloride containing solutions. Freeze-dried powder: The compound may be stored for 3 years at room temperature protected from light. Reconstituted solution: In 5% dextrose solution or sterile Water for Injection in the original vial, the solution may be stored for 24 to 48 hours at 2-80° C. Infusion solution: after dilution in 5% dextrose solution, the shelf-life is 24 hours at room temperature.

10.3.8 Administration

Antiemetic premedication (5-HT3 blocker with or without dexamethasone) is recommended. Cold temperatures can precipitate/exacerbate neurological symptoms-avoid during the infusion of oxaliplatin. Never reconstitute/dilute with a chloride-containing solution; avoid aluminum parts when preparing/mixing oxaliplatin. Incompatible with alkaline media (i.e., solutions of 5-fluorouracil). Prepare oxaliplatin in 250-500 mL D5W.

11 STUDY CALENDAR

	Screening ⁴	During Radiotherapy	Day 1 of Each Cycle of Chemotherapy ⁸	Completion of Chemotherapy ¹⁰	10 to 14 Months after Radiotherapy	Long-term Follow-up ⁹
Informed consent	X					
H&P	X	X (once)	X	X	X	
CBC diff, plts	X	X (once)	X			
CMP	X		X			
Pregnancy test ⁵	X ⁶					
Colonoscopy or barium enema or Hypaque enema	X ¹¹					
Surgical assessment with proctoscopy or sigmoidoscopy				X		
Digital rectal exam	X			X		
Staging study to evaluate disease in abdomen and pelvis ¹	X					
Staging study to evaluate disease in lungs ²	X					
Imaging study to assess local extent of primary tumor ³	X			X		
Radiotherapy		X ⁷				
FOLFOX / CAPEOX			X			
FACT-C	X			X	X	

AE assessment	AEs should be collected through 1 year following the start of RT	
---------------	--	--

1. CT with contrast or MRI or PET/CT or PET/MRI
2. Chest x-ray or CT of the chest or PET/CT
3. Pelvic MRI (preferred), endorectal ultrasound, MRI, CT scan
4. Within 8 weeks of day of simulation for RT but no later than the first radiation treatment
5. Women of childbearing potential only
6. No more than 14 days prior to the first day of treatment
7. 5 fractions delivered over the course of 5 days (preferably starting on a Monday). Optional concomitant boost may be delivered to the primary tumor of 1-2 Gy per day (30-35 Gy to tumor total). If a boost is given then the maximum allowed dose to small bowel is 25 Gy.
8. Chemotherapy should start 2 to 4 weeks after the end of RT. Each cycle is 14 days; a total of 8 cycles of chemotherapy will be given
9. Long-term follow-up will be done per routine policies of the treating physicians. It is recommended that there be follow up visits every 6 months with clinical exam until 5 years from study enrollment. Data will be collected from the medical record every 6 months on progression/recurrence and survival.
10. 3-8 weeks after the end of chemotherapy
11. Within 12 weeks of day of simulation for RT but no later than the first radiation treatment

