5.3 Completion of Chemotherapy/Post-Treatment Evaluation

Two to four weeks after completion of chemotherapy, patients will have the following assessments:

- FACT-C questionnaire.
- Surgical assessment w/ endoscopy (sigmoidoscopy preferred, rigid proctoscopy acceptable) to evaluate the extent of residual tumor
- MRI (when feasible) to evaluate ycT stage
- DRE (when feasible) to evaluate ycT stage

For patients with a cCR, non-operative management will be pursued. Patients will be assessed for sustained cCR by pelvic MR, endoscopy (sigmoidoscopy preferred, rigid proctoscopy accepted) and DRE every three months (not necessarily on the same day / appointment) for 1 year. Follow-up after 1 year will be left to the discretion of the treating physician, although DRE, pelvic MR and endoscopy every 3-4 months is recommended for the second year. CT chest/abdomen/pelvis every 6 months is recommended for at least the first 2 years. For patients with residual disease who do not meet criteria for cCR by 4 weeks after completion of the 8th cycle of FOLFOX, further therapy is mandated and at the discretion of the treating physicians. Patients whose disease is amenable to transanal endoscopic microexcision (TEM) or local excision (LE) may undergo TEM/LE to evaluate degree of residual disease. For those with pT1 disease without LVSI present, non-operative management may continue with evaluation noted above. For those with residual T2-3 disease or T1 with LVSI, extirpative surgery including TME is recommended with treatment at investigators discretion proceeding off-study.

Post-treatment lymph nodes are to be evaluated by imaging and reviewed in multidisciplinary tumor board with a radiologist and classified as progressive, persistent disease, indeterminate or benign. Patients with progressive or persistent lymph node disease will not be eligible for non-operative management and will undergo additional therapy. Patients with indeterminate or benign lymph nodes AND cCR of primary will undergo non-operative management.

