7 CHEMOTHERAPY GUIDELINES

7.1 Chemotherapy Schedule and Doses

Chemotherapy should begin 2 to 4 weeks after completion of radiotherapy and will consist of 5FU/leucovorin/oxaliplatin every other week for 8 courses (16 weeks). Alternatively, capecitabine/oxaliplatin (CAPE PO 1000 mg/m² BID days 1-14 Q21 days, oxaliplatin IV 130 mg/m² IV Q21 days on day 1) x 5 cycles over 15 weeks may be administered instead of FOLFOX. A maximum (total) delay of treatment of 4 weeks is allowed per protocol due to factors/AEs listed in this section. Cumulative delays in excess of 4 weeks will need to be discussed with the Principal Investigator. Such cases will need to be individualized depending on the clinical scenario.

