7.2 Agent Administration

Folfox	Dose	Route	Schedule
Oxaliplatin*	85 mg/m ²	IV over 2 hours	On Day 1, Q 14 days
Leucovorin*	400 mg/m ²	IV over 2 hours	On Day 1, Q 14 days
5-FU Bolus*	400 mg/m ²	IV push	On Day 1, Q 14 days
5-FU Infusion*	2400 mg/m ²	IV CIIV	On Day 1, Q 14 days over 46 hours

*Administer sequentially as written, except oxaliplatin and leucovorin may be administered concurrently

CapeOx	Dose	Route	Schedule
Oxaliplatin	130 mg/m ²	IV	On Day 1, Q 21 days
Capecitabine	1000mg/m ²	PO BID	On Days 1-14, Q 21 days

Dose calculations should be based on actual weight and not corrected for obesity.

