16.4 Definition of Evaluability

Patients who have completed all radiotherapy and chemotherapy will be considered evaluable for analysis. Patients who are inevaluable for the primary endpoint will be replaced.

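### The study calendar applies 14-day cycles and a total of 8 to CapeOx, which Section 7 gives as five 21-day cycles, so the CapeOx schedule and its completion can each be read two ways

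*Combined protocol and SAP*

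**What the plan says.** Section 7.1 sets FOLFOX at 8 fortnightly courses over 16 weeks. It then allows capecitabine/oxaliplatin as an alternative, "x 5 cycles over 15 weeks may be administered instead of FOLFOX". The Section 7.2 table confirms the CapeOx interval, with capecitabine given "On Days 1-14, Q 21 days" and oxaliplatin on day 1 of the same 21-day cycle.

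The study calendar (Section 11) has a single row, "FOLFOX / CAPEOX". It is marked only in the column "Day 1 of Each Cycle of Chemotherapy", and that column carries footnote 8: "Each cycle is 14 days; a total of 8 cycles of chemotherapy will be given". The footnote names no regimen and makes no exception.

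Three other places bear on the point:

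- The primary objective specifies 8 cycles of multi-drug chemotherapy in the front matter and in Sections 2.1 and 16.1. The opening of Section 2 also says 8 cycles. None mentions a 5-cycle alternative.
- In Section 5.3, the clause on patients with residual disease fixes the time for further therapy "by 4 weeks after completion of the 8th cycle of FOLFOX".
- Section 16.4 states: "Patients who have completed all radiotherapy and chemotherapy will be considered evaluable for analysis". It gives no cycle count and says that inevaluable patients are replaced. The interim rule in Section 16.3 likewise counts patients who complete both treatments.

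**The concern.** Footnote 8 cannot be true for a CapeOx patient if Section 7 is true. The calendar row names CapeOx, so the calendar claims to cover it, and the documents do not say which section prevails.

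Two things are at stake. The first is conduct. Staff who plan from the calendar and staff who plan from Section 7 would book different day-1 visits, blood tests and drug administration for the same patient, and would expect different numbers of chemotherapy forms (Section 12 asks for one at the end of each cycle). Sections 4, 9 and 17 provide for secondary sites, and Section 15 audits adherence to the protocol, so the two readings could coexist across sites.

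The second is analysis. Evaluability depends on having completed chemotherapy, and the documents hold two possible totals for CapeOx. If the choice between them were made for an individual patient after the response was known, it could bias who is counted.

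**Working it through.** Inputs: FOLFOX 14 days x 8 (Section 7.1); CapeOx 21 days x 5 (Sections 7.1 and 7.2); calendar 14 days x 8 (Section 11, footnote 8); 20 evaluable patients with a threshold of 6 (Sections 16.1 and 16.2); interim rule on 10 patients (Section 16.3).

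**Step 1: reproduce the stated durations.** Weeks = cycles x days per cycle / 7.

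- FOLFOX: 8 x 14 / 7 = 16 weeks, as stated.
- CapeOx: 5 x 21 / 7 = 15 weeks, as stated.

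Section 7.1 is internally consistent for both regimens, and footnote 8 agrees with it for FOLFOX.

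**Step 2: apply footnote 8 to CapeOx.**

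| | Sections 7.1 and 7.2 | Footnote 8 |
|---|---|---|
| Days per cycle | 21 | 14 |
| Cycles | 5 | 8 |
| Duration | 15 weeks | 8 x 14 / 7 = 16 weeks |
| Day-1 visits | 1, 22, 43, 64, 85 | 1, 15, 29, 43, 57, 71, 85, 99 |
| Per-cycle forms | 5 | 8 |

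Only days 1, 43 and 85 coincide. Keeping the 21-day interval and taking only the count of 8 from the footnote does not help: 8 x 21 / 7 = 24 weeks, against 15. Keeping 5 cycles and taking the 14-day length gives 5 x 14 / 7 = 10 weeks. No combination that uses either element of the footnote gives the 15 weeks of Section 7.1. A 14-day cycle also does not fit capecitabine on days 1 to 14 of a 21-day cycle, because 21 - 14 = 7 days of the printed cycle would disappear.

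**Step 3: completion.** A patient who has had all 5 CapeOx cycles is complete under Section 7.1 and 8 - 5 = 3 cycles short under footnote 8 and the objective. Section 16.4 does not choose between these totals.

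**Step 4: effect on the decision rule.** Inevaluable patients are replaced, so the final denominator stays at 20 and the threshold at 6/20 = 30%. Swapping one patient for another can move the count by at most one success, or 1/20 = 5 percentage points (at the interim, 1/10 = 10 points). Planned accrual is 22 (Section 16.6), leaving 22 - 20 = 2 places for inevaluability from any cause. The documents do not state how many patients are expected to receive CapeOx, so the number of such swaps cannot be estimated.

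**The case against.** The strongest reply is that a careful reader would follow Section 7. It is the only place that attaches a cycle count to CapeOx by name, and Section 5.2 sends readers there for chemotherapy guidance. On that view, completing chemotherapy means completing the course set for the regimen given, and footnote 8 is a FOLFOX note that was not extended when CapeOx was allowed. That is probably how the conflict arose. It does not remove it: the calendar row names CapeOx, the footnote is an operative instruction, the objectives repeat the 8-cycle figure, and nothing gives Section 7 precedence.

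The reply does succeed against four stronger readings that a reader might infer:

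- *The denominator changes.* It does not. Figures such as 6/19 would arise only before replacement.
- *Every CapeOx patient's evaluability is in doubt.* A patient becomes inevaluable only if someone lets the footnote override Section 7.1, and there may be no CapeOx patients at all.
- *CapeOx patients have no time point for response assessment.* Section 5.3 opens with a window of two to four weeks after chemotherapy ends, whatever the regimen, and calendar footnote 10 also counts from the end of chemotherapy. Only the later clause on further therapy for residual disease names FOLFOX.
- *The calendar directs 60% more oxaliplatin.* The arithmetic (8 x 130 = 1040 against 5 x 130 = 650 mg/m²; 1040/650 = 1.60) is right, but the calendar prints no chemotherapy dose. A reader would have to take 130 mg/m² from Section 7.2 and ignore the 21-day interval in the same row.

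**Conclusion.** The contradiction is real: footnote 8 is wrong for CapeOx if Sections 7.1 and 7.2 are right, and the 8-cycle objectives and the FOLFOX-specific clause in Section 5.3 do not fit CapeOx either. This is more than an editorial slip, because it leaves two working schedules for a permitted regimen and two meanings of completion in the evaluability and interim rules.

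Its size is limited. The per-patient discrepancy is 3 cycles and 7 days per cycle. The analysis effect is on which patients are among the 20, and it arises only if CapeOx is used and completion is judged against 8 cycles. The sample size and the 6/20 threshold stand. The documents do not show that any patient would be misdosed or misclassified; they show that the text permits inconsistent handling.

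**What to change.** Reconcile calendar footnote 8, the objective wording (front matter, Sections 2, 2.1 and 16.1) and the residual-disease clause in Section 5.3 with Sections 7.1 and 7.2, so that each regimen has one stated cycle length and one stated number of cycles throughout. In Section 16.4, state that completion of chemotherapy is judged against the course that the reconciled protocol specifies for the regimen the patient received, and use the same definition in Section 16.3. The sponsor's clinicians must decide which schedule, and which wording of the Section 5.3 clause, is correct.

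The cost is a wording amendment, with no added patients or procedures.

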12 DATA SUBMISSION SCHEDULE

Case report forms with appropriate source documentation will be completed according to the schedule listed in this section.

Form	Completion Schedule
On-Study Form	Time of registration
Radiation Therapy Form	Completion of RT
Chemotherapy Form	At the end of each cycle of chemotherapy
RECIST Form	Baseline Completion of chemoradiation
Follow-Up Form	1 year after the start of RT
FACT-C	Baseline Completion of chemoradiation 10-14 months after chemoradiation
Long-Term Follow-Up Form	Every 6 months for 5 years after the start of RT
Adverse Events Form	Ongoing

Any queries generated by Washington University must be responded to within 28 days of receipt by the participating site. The Washington University research team will conduct a regular review of data status at all secondary sites, with appropriate corrective action to be requested as needed.

13 MEASUREMENT OF EFFECT

Criteria for complete clinical response:

- No residual gross tumor at procto/sigmoidoscopy, or only erythematous scar or ulcer
- No palpable tumor on DRE
- No radiographic evidence of tumor on MRI
- No suspicious mesorectal lymph nodes on MRI
- Negative biopsy from scar, ulcer, or former tumor site (if necessary according to surgeon's judgment)

Criteria for no significant clinical response:

- Residual disease by DRE, endoscopy or MR.
- Increase in primary tumor size upon clinical exam or imaging
- Any new lesions

14 DATA AND SAFETY MONITORING PLAN

Outcome, including response rates and patient morbidity, will be reviewed by the principal investigator with the medical oncology and surgery co-investigators ([name]) every six months.

In compliance with the Washington University Institutional Data and Safety Monitoring Plan, the Principal Investigator will provide a Data and Safety Monitoring (DSM) report to the Washington University Quality Assurance and Safety Monitoring Committee (QASMC) semi-annually beginning six months after accrual has opened (if at least five patients have been enrolled) or one year after accrual has opened (if fewer than five patients have been enrolled at the six-month mark).

The Principal Investigator will review all patient data at least every six months, and provide a semi-annual report to the QASMC. This report will include:

- HRPO protocol number, protocol title, Principal Investigator name, data coordinator name, regulatory coordinator name, and statistician
- Date of initial HRPO approval, date of most recent consent HRPO approval/revision, date of HRPO expiration, date of most recent QA audit, study status, and phase of study
- History of study including summary of substantive amendments; summary of accrual suspensions including start/stop dates and reason; and summary of protocol exceptions, error, or breach of confidentiality including start/stop dates and reason
- Study-wide target accrual and study-wide actual accrual including numbers from participating sites
- Protocol activation date at each participating site
- Average rate of accrual observed in year 1, year 2, and subsequent years at each participating site
- Expected accrual end date, accrual by site
- Objectives of protocol with supporting data and list the number of participants who have met each objective
- Measures of efficacy
- Early stopping rules with supporting data and list the number of participants who have met the early stopping rules
- Summary of toxicities
- Abstract submissions/publications
- Summary of any recent literature that may affect the safety or ethics of the study

The study principal investigator and Research Patient Coordinator will monitor for serious toxicities on an ongoing basis. Once the principal investigator or Research Patient Coordinator becomes aware of an adverse event, the AE will be reported to the HRPO and QASMC according to institutional guidelines.

